20.0 Compensation for Research-Related Injury

PROTOCOL TITLE: Feasibility of Brief Intervention for HIV+ Adults 50+ in Primary Care Settings

N/A

21.0 Economic Burden to Subjects

N/A

22.0 Consent Process

All participants will be required to read detailed consent forms prior to participation. Then the Research Assistant who will be consenting the participant will address all of the major details of the study. Before signing, participants will be given the opportunity to ask any questions they may have about the study. Participants are advised of the voluntary nature of participation and of their right to withdraw from the project at any time and their right to require that information about themselves be removed from data analysis. Each study participant receives a verbal and written description of the study.

Non-English Speaking Subjects

- *N/A*

Waiver or Alteration of Consent Process (consent will not be obtained, required information will not be disclosed, or the research involves deception)

- *N/A*

Subjects who are not yet adults (infants, children, teenagers)

- *N/A*

Cognitively Impaired Adults

- *N/A*

Adults Unable to Consent

- *N/A*

23.0 Process to Document Consent in Writing

Participants will sign an IRB approved informed consent document. Before signing, participants will be given the opportunity to ask any questions they may have about the study. Participants are advised of the voluntary nature of participation and of their right to withdraw from the project at any time.

24.0 Setting

Recruitment/Sampling: Patients will be recruited using convenience sampling technique from HIV primary care clinics with whom the PI works regularly: the Columbia County Department of Health (Lake City, FL) and the CAN Community Health Clinic

PROTOCOL TITLE: Feasibility of Brief Intervention for HIV+ Adults 50+ in Primary Care Settings

(Jacksonville, FL). The PI has dedicated space in these locations to conduct all study activities.

25.0 Resources Available

Since SBIRT is intended to be a universal intervention within a targeted setting, all adults (18+) who are being seen in clinic will be screened using validated screening instruments as part of routine care. Scores and the nature of the follow up (i.e., referred to brief intervention or no intervention needed) will be documented in the electronic medical record. We will train all recruiters and clinic staff to provide an extensive explanation of why we are offering these services, as the patients may not perceive themselves as having a substance misuse issue.

Universal Screening Procedures

Screening is intended to identify individuals at varying levels of risk associated with the use of alcohol and/or drugs. It is not intended to provide a formal diagnosis (which is the function of clinical assessment), but rather to provide guidance for deciding which level of intervention may be needed to address the identified level of risk. The ASSIST is an eight-item instrument developed by the World Health Organization (WHO) to screen for hazardous, harmful, and dependent use of alcohol, tobacco, and drugs. The ASSIST typically takes about 5-10 minutes to administer, although it can take longer depending on the number of drugs used over the lifetime. For each drug endorsed, questions are asked about frequency of use, problems related to use, dependence indicators, and injection drug use in the three months prior to the current administration of the instrument. Following ASSIST administration, separate risk scores are calculated, with scores falling within a low-, moderate-, or high-risk range. Table 1 shows the risk-level scores for alcohol and drugs and the indicated intervention for each risk level, as specified in the WHO brief intervention manual. We will use a computer based version of the ASSIST to make the screening faster to administer and score (see link below).

<https://www.drugabuse.gov/nmassist/>

Table 1 ASSIST risk scores and level of intervention

	ASSIST Alcohol Score	Assist Drug Score	Intervention
Low Risk	0 – 10	0 – 3	Feedback on ASSIST score, literature
Moderate Risk	11 – 26	4 – 26	Feedback on ASSIST score, literature, brief intervention
High Risk	27+	27+	Feedback on ASSIST score, literature, brief intervention, referral to treatment

Retention

Attrition is a significant concern in an implementation trial. First, we will develop a strong collaborative relationship between participants and members of the research team. This is a critical component of our retention strategy, beginning at the moment of first contact between the recruiter and potential participant. Second, we will ensure that participants understand that they are making a contribution and that their efforts have the potential to improve other people's experiences. Participants will receive study newsletters and flyers containing useful and pertinent information on wellness management and other related resources and local events. Finally, we will obtain secondary contact information and will use multiple communication channels (email, phone, text messaging, social media) to maintain contact with study participants. We have budgeted research staff time for tracking and follow-up of participants. One RA will dedicate 20% time to patient tracking during recruitment and follow up phase. Based on our prior work using these strategies with this patient population, we anticipate a 10% dropout rate with a maximum dropout rate of 20% by time 3.

Follow-up visits will be scheduled 4-6 weeks in advance of the next study appointment. Participants will then be contacted with assessment visit reminders within the week before their 3-month and 6-month visits. If participants cannot be reached by phone, a voicemail will be left listing the day and time of the scheduled visit along with instructions to call and reschedule if the participant is no longer available at the scheduled day and time. Participants who do not attend their assessment visit will be called 15 minutes after the anticipated start time of the visit and asked to reschedule. If the participant does not answer the phone, a voicemail will be left and an email sent asking the participant to call our study staff to reschedule their visit. Participants will be contacted up to 5 times to reschedule. Participants who cannot be reached will be sent a registered letter through the USPS reminding them of the final assessment visit and asking them to contact study staff to schedule. We will also use clinical schedules from our research partner clinics to monitor for participant return visits to clinic and use these visits as an opportunity to reengage with study participants. We will continuously review and examine our retention strategies to ensure that they meet participant approval and are maximally effective.

26.0 Multi-Site Research*

+++Per NIH policy research funded via Career Development Awards, such as the current study are NOT subject to the NIH single IRB policy due to the scope of the research award. The current research is funded via a career development award from NIDA under grant 1K23DA039769-04.

See section C item 6 in the link below.

PROTOCOL TITLE: Feasibility of Brief Intervention for HIV+ Adults 50+ in Primary Care Settings

https://grants.nih.gov/grants/policy/faq_single_IRB_policy_research.htm#5180

PROTOCOL TITLE:

Feasibility of Brief Intervention for HIV+ Adults 50+ in Primary Care Settings

PRINCIPAL INVESTIGATOR:

[name], Florida State University

NCT03057119

DATE OF DOCUMENT:

6/15/2022

Statistical Analysis Plan

Aim 1 (Feasibility): The model will be considered feasible if 80% of the target population has been reached.

Primary Outcome

Feasibility Calculation. Feasibility is defined as the extent to which the intervention can be successfully used or carried out within the UF Health Infectious Disease-Medical Specialties Clinic. Therefore, we will calculate feasibility using the following steps (see link to method for calculation below):

- **Step 1:** Enumerating all potential participants in target population. The target population will be defined as all patients seen by [name] seen during study period.
- **Step 2:** Quantify Exclusions. List reasons for and number of exclusions.
- **Step 3:** Quantify missed cases. List number of lost cases or missed due to lack of staff resources, etc.
- **Step 4:** Quantify Eligible Participants. List number of known eligible participants who were offered participation.
- **Step 5:** Quantify number of Patients Reached. Divide number of participants enrolled to determine percent participation.
- **Step 6:** Report most common reasons for declining participation.

<http://re-aim.org/resources-and-tools/calculations/calculating-and-reporting-on-reach/>

Acceptability Questionnaire. This 10-item questionnaire (1 = not acceptable to 5 = highly acceptable) queries the participant on the acceptability of the program. Item content includes the following:

1. Program was a good use of my time
2. Program was helpful
3. Program will be useful in my daily
4. Likeability of interventionist
5. Clinical skill of interventionist
6. Likeability of assessor
7. Ease of participation in assessments
8. Ease of participation in intervention
9. Interactions with program staff
10. Overall rating.

To examine ratings of acceptability, we will use the overall acceptability score and percentage of acceptability. Overall acceptability will be assessed by summing ratings from the 10-item questionnaire to provide a total intervention acceptability score for the intervention, such that acceptability scores for the intervention could range from 10 (low acceptability) to 50 (high acceptability). The intervention will be considered to have acceptability if 80% of the participants rank the intervention as acceptable (i.e., 4 or higher) on 80% or more of the scale items. We will then examine each question of the Acceptability Questionnaire separately to determine strengths and weaknesses of the intervention.

Aim 2a and 2b (Acceptability): Acceptability scores will be calculated for all participants as listed above to determine overall acceptability of the SBIRT model. Sub analyses will be conducted for disease type and HIV x age using calculations listed above. Acceptability will be examined by disease type HIV vs. non-HIV. Acceptability will also be examined for HIV only by younger (≤ 49) versus older (≥ 50).

Aim 3: We will clean the data, examine variable distributions, compute descriptive statistics, examine outliers, and examine the effectiveness of randomization prior to analyses of specific aims to ensure the underlying assumptions of normality and equal variance have not been violated. Before testing each secondary outcome, we will examine whether intervention and control group participants differ on potential confounding variables at study entry. We will control for a variable if it differs by condition on the outcome variable being tested in that analysis at $p < .05$. Using chi-square (or t-test for continuous variables) we will examine the associations between the dependent variables and relevant demographic variables. All analyses will employ an intent-to-treat approach.

Our first step will be to see if the intervention influenced formal engagement in substance use treatment. Using chi-square analyses we will examine group difference on engagement in formal treatment (0=no treatment/1=treatment confirmed). To test the remainder of the hypothesis, analyses will rely on mixed model repeated measures ANOVA since the relatively small sample size is likely to prohibit more sophisticated statistical modeling. Hypotheses testing rely on inspection of F values and associated p values. A mixed model ANOVA is used to test for differences between two or more independent groups while subjecting participants to repeated measures. In the current analyses the fixed effect will be group condition (SBIRT-PN or TAU) and the random effect will be number of drug use days in the past 3 and 6 months.

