1.0 Study Summary

Study Title	Feasibility of Screening, Brief Intervention for HIV+ Adults 50+ in Primary Care Settings
Study Design	We will use a repeated measures randomized control trial design to compare patient outcomes at baseline as well as 3 and 6 months post-intervention.
Primary Objective	Feasibility and Acceptability of intervention
Secondary Objective(s)	Substance misuse
Research Intervention(s)	Screening, Brief Intervention, Referral to Treatment with Peer Navigator (SBIRT-PN)
Study Population	HIV+
Sample Size	90
Study Duration for individual participants	6 months
Study Specific Abbreviations/ Definitions	SBIRT-PN = Screening, Brief Intervention, Referral to Treatment with Peer Navigator

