2.0 Objectives*

In order to develop effective substance use intervention models for HIV care settings the specific aims of the current project are:

Aim1: Examine the feasibility of implementing the SBIRT-PN model in Infectious Disease-Medical Specialties Clinics in the state of Florida.

H1: We hypothesize that the SBIRT-PN model will demonstrate high feasibility as evidenced by at least 80 % of the total N having screenings.

Aim2a: Assess the acceptability of SBIRT-PN.

H2a: We hypothesize that SBIRT-PN will demonstrate high acceptability among patients enrolled in this condition.

Aim2b: Assess the acceptability of SBIRT-PN among HIV-positive individuals by age cohort (younger vs older).

H2b: We hypothesize that SBIRT-PN will demonstrate higher acceptability among older HIV-positive patients enrolled in this condition.

Aim3: Assess influence of SBIRT-PN model on treatment engagement and substance use compared to enhanced treatment as usual (TAU).

H3: We hypothesize that those in the SBIRT-PN condition will evidence greater treatment engagement and a reduction in substance use.

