4.0 Study Endpoints*

Primary Outcome

Feasibility Calculation. Feasibility is defined as the extent to which the intervention can be successfully used or carried out within the UF Health Infectious Disease-Medical Specialties Clinic. Therefore, we will calculate feasibility using the following steps (see link to method for calculation below):

- **Step 1:** Enumerating all potential participants in target population. The target population will be defined as all patients seen by [name] seen during study period.
- **Step 2:** Quantify Exclusions. List reasons for and number of exclusions.
- **Step 3:** Quantify missed cases. List number of lost cases or missed due to lack of staff resources, etc.
- **Step 4:** Quantify Eligible Participants. List number of known eligible participants who were offered participation.
- **Step 5:** Quantify number of Patients Reached. Divide number of participants enrolled to determine percent participation.
- **Step 6:** Report most common reasons for declining participation.

<http://re-aim.org/resources-and-tools/calculations/calculating-and-reporting-on-reach/>

Acceptability Questionnaire. This 10-item questionnaire (1 = not acceptable to 5 = highly acceptable) queries the participant on the acceptability of the program. Item content includes the following:

PROTOCOL TITLE: Feasibility of Brief Intervention for HIV+ Adults 50+ in Primary Care Settings

1. Program was a good use of my time
2. Program was helpful
3. Program will be useful in my daily
4. Likeability of interventionist
5. Clinical skill of interventionist
6. Likeability of assessor
7. Ease of participation in assessments
8. Ease of participation in intervention
9. Interactions with program staff
10. Overall rating.

To examine ratings of acceptability, we will use the overall acceptability score and percentage of acceptability. Overall acceptability will be assessed by summing ratings from the 10-item questionnaire to provide a total intervention acceptability score for the intervention, such that acceptability scores for the intervention could range from 10 (low acceptability) to 50 (high acceptability). The intervention will be considered to have acceptability if 80% of the participants rank the intervention as acceptable (i.e., 4 or higher) on 80% or more of the scale items. We will then examine each question of the Acceptability Questionnaire separately to determine strengths and weaknesses of the intervention.

Secondary Outcomes

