5.0 Study Intervention

Intervention Procedures: The 30 minute intervention session will cover the following content: 1) Psycho-educational content (5 minutes): The interventionist will discuss substance use and misuse, HIV, and the interaction of aging and substance use (e.g. greater intoxication effects with lower amounts). 2) Readiness Assessment (10 minutes): The interventionist will give the patient feedback on their NM-ASSIST score and assess the patient's readiness to change based on Prochaska's stages of change. 3) Goal-Setting (5 minutes): The interventionist will use motivational interviewing techniques to identify the patients' most salient reasons for addressing substance use issues. 4) Identifying and prioritizing needs (5 minutes): The interventionist will use problem-solving techniques to help patients identify which services may best help them work

PROTOCOL TITLE: Feasibility of Brief Intervention for HIV+ Adults 50+ in Primary Care Settings

towards their goals. Services will include (but are not limited to) emergency crisis services, counseling to deal with substance use, referral to local self-help groups (Alcoholics Anonymous, Narcotics Anonymous, etc.), legal assistance, faith-based counseling, or mental health counseling. 5) Assignment of Peer Navigator and Session wrap (5 minutes): The interventionist will use a referral resource guide to provide the contact information of agency representatives and help the patient formulate a plan for follow-up.

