6.0 Procedures Involved*

Recruitment/Sampling: Patients will be recruited using convenience sampling technique from HIV primary care clinics with whom the PI works regularly: the Columbia County Department of Health (Lake City, FL) and the CAN Community Health Clinic (Jacksonville, FL)

Preliminary Screen: Patients will be prescreened for eligibility using a computerized screening tool, NIDA Modified Alcohol, Smoking, Substance Involvement Screening Test [NM-ASSIST], to assess substance misuse risk level. All clinic patients will have the opportunity to complete the substance use screening assessment after checking in for their appointment. All who score moderate and above on the alcohol or illicit substance portion of the NM-ASSIST and meet eligibility criteria will be referred to the study. We will train all recruiters (clinic staff) to provide an extensive explanation of why we are offering these services, as the patients may not perceive themselves as having a substance misuse issue.

Baseline Assessment Procedures: Following a successful initial screen, study staff will explain the procedures of the study and obtain informed consent. All study activities will be conducted in a private room in the clinic. The research assistant (RA) performing the assessment will verify the patient's complete understanding of the informed consent form and all study procedures. Following informed consent, patients will complete the baseline assessment. The baseline assessment will consist of urine drug screen and a series of research questionnaires delivered on a mobile device. The research questionnaires include information on: substance use, substance use treatment, HIV treatment engagement, depression, and pain. The assessment is relatively brief in order to maximize willingness to participate and decrease patient burden. The assessment will take approximately 30 minutes to complete. The questionnaires will be given in a computerized. The iPad/tablet will use REDCap survey software, which provides direct, encrypted transfer of information via internet to a secure study server.

Three and Six Month Follow-Up Assessment: *Participants will be contacted three and six months post-intervention to schedule an in-person follow-up assessment. We will evaluate substance use treatment engagement post intervention and substance use (self-report and urine toxicology analysis). Participants will be compensated \$30 for each*

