10.0 Subject Population*

Participants will be 90 patients recruited through DOH Columbia County and CAN Community Health.

Study inclusion criteria includes that patients must be:

1. HIV-positive (seropositive confirmed by medical records).
2. Arrive for a clinic visit with an HIV physician.
3. Have a substance misuse screening score indicating moderate or high risk.

Persons will be ineligible if they:

1. are unable to interview and consent in English
2. unwilling or unable to participate in follow up
3. currently in addiction treatment
4. have a medical marijuana prescription

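### The 80% feasibility rule is defined inconsistently within the protocol and the SAP repeats it unresolved, so the same counts can give opposite conclusions

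*SAP*

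**What the plan says.** The primary objective in protocol section 1.0 is "Feasibility and Acceptability of intervention". Acceptability has its own 80% criterion. For feasibility the documents give the following.

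- **H1, protocol section 2.0:** "high feasibility as evidenced by at least 80 % of the total N having screenings".
- **Analysis rule, SAP Aim 1 and protocol section 17.0:** "The model will be considered feasible if 80% of the target population has been reached".
- **Calculation steps, protocol section 4.0 and SAP (same text):** Step 1 defines the target population as all patients seen by a named party over the study period. Step 3 counts missed cases. Step 4 counts known eligible patients who were offered participation. Step 5, labelled as the number of patients reached, divides the number enrolled but does not say by what. No step records the number screened. A web page is linked for the method.
- **Screening, protocol section 6.0:** "All clinic patients will have the opportunity to complete the substance use screening assessment after checking in for their appointment". Section 25.0 describes screening of all adults in clinic as routine care.
- **Entry, protocol section 10.0:** a screening score in the moderate or high range is an inclusion criterion.
- **Place:** section 4.0 and the SAP define feasibility as the extent to which the intervention can be "successfully used or carried out within the UF Health Infectious Disease-Medical Specialties Clinic". Section 10.0 says "Participants will be 90 patients recruited through DOH Columbia County and CAN Community Health", and sections 6.0 and 24.0 name the same two sites.

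**The concern.** The 80% figure is attached to two different numerators, screened and enrolled, and to more than one possible denominator. These are different quantities: one describes uptake of a universal screen, the other participation in a randomised trial. Because this is the only success rule for feasibility, the choice of ratio decides a primary conclusion. If the choice is left open until the counts are known, a favourable ratio can be selected, and a reader cannot tell which one was prespecified.

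A secondary problem is that the definition ties feasibility to a clinic where, on the documents' own account, nobody is recruited. The setting in which the conclusion is meant to hold is therefore also unclear.

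**Working it through.** The plan gives no feasibility calculation to reproduce, so the check is to set out the readings and see whether they can disagree.

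**Inputs from the documents:** threshold 80% (section 2.0, section 17.0, SAP Aim 1); planned enrolment 90 (sections 1.0, 10.0 and 12.0); a qualifying screen required for entry (section 10.0). Patients seen, screened and offered are not stated.

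**Four readings**

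- (a) Screened / seen. This interprets H1's total N as the patients seen, which the universal screening in sections 6.0 and 25.0 supports.
- (b) Enrolled / eligible and offered. This is Step 5 with Step 4 as its divisor, suggested by the order of the steps.
- (c) Enrolled / all patients seen. This is the Aim 1 sentence taken with Steps 1 and 5.
- (d) Screened / 90 enrolled. This takes H1's total N as the study sample, which is how section 12.0 uses N.

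**Reading (d).** Everyone enrolled has been screened, so the ratio is 90/90 = 100% whatever happens in the clinics.

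**Reading (c).** If those enrolled come from the Step 1 population, then enrolled ≤ eligible, so enrolled/seen ≤ eligible/seen. A pass therefore needs eligible/seen ≥ 80% at any volume. With exactly 90 enrolled, 90/0.80 = 112.5, so at most 112 patients may be seen: 90/112 = 80.4% passes and 90/113 = 79.6% fails.

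**Ordering.** Those enrolled are a subset of those screened and of those offered, and both of these are subsets of those seen. Hence (c) ≤ (a) ≤ 100% and (c) ≤ (b) ≤ 100%. Readings (a) and (b) use different counts, so neither implies the other.

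**Illustration (assumed flows, chosen to show that the verdict can reverse):**

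| Flow | Seen | Screened | Offered | Enrolled | (a) | (b) | (c) | (d) |
|---|---|---|---|---|---|---|---|---|
| A | 400 | 330 | 120 | 90 | 82.5% pass | 75.0% fail | 22.5% fail | 100% pass |
| B | 400 | 300 | 110 | 90 | 75.0% fail | 81.8% pass | 22.5% fail | 100% pass |

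The arithmetic is 330/400, 90/120, 90/400 and 90/90 for A, and 300/400, 90/110, 90/400 and 90/90 for B.

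**Range.** Over an assumed 150 to 600 patients seen with 90 enrolled, (c) falls from 90/150 = 60% to 90/600 = 15%. Over the same range (a) passes if at least 0.8 × 150 = 120 to 0.8 × 600 = 480 are screened, whatever the enrolment.

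**The case against.** Several points on the other side have force.

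- **The Aim 1 sentence does name a denominator.** It is the target population, which Step 1 defines. This stands: a reader might infer that the rule has no divisor at all, but only Step 5's sentence lacks one. Taking Step 1 as the divisor, however, gives reading (c), which counts every low-risk or excluded patient as not reached and still conflicts with H1.
- **The order of the steps, and the linked page, may settle Step 5.** The order does point to enrolled over offered. The page was not available to this review. Even if it gives that divisor, an enrolment ratio does not become H1's screening ratio.
- **The steps already require most of the counts.** A reader could recompute (b) and (c) from the reported steps, which limits the scope for selection. The number screened is the gap; Step 1 minus Step 3 approximates it only if missed cases means patients not screened.
- **The clinic name changes no ratio.** This is correct, and it is why the point is secondary. The general reference in Aim 1 to such clinics in Florida does not cure an operational definition that names a different clinic.

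Three stronger readings are tempting. A reader might infer that the SAP departs from the protocol. It does not: section 4.0 and section 17.0 carry the same steps and rule, so the protocol contradicts its own H1 and the SAP copies it. A reader might infer that H1 plainly means screened over seen. The documents do not say so, and they use N for the sample of 90. A reader might also treat the flows above as evidence that the readings will diverge. They show only that divergence is possible.

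The removed name in Step 1 is not an error in the plan. It does mean that one cannot tell from the text whether that population covers both recruiting clinics.

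**Conclusion.** The point holds. The protocol sets one 80% threshold on two incompatible quantities, and the SAP repeats the unresolved version. Depending on the reading, the feasibility criterion runs from met by construction (d) to out of reach unless at least 80% of patients seen are eligible (c). The two more sensible readings, (a) and (b), can give opposite answers on the same counts.

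The result for (d) and the eligibility bound for (c) need no assumption about clinic volume; the bound does assume that enrolled patients belong to the Step 1 population. The 112-patient limit assumes that enrolment reaches exactly 90. How likely the readings are to disagree in practice cannot be judged from the documents. Because this is the only feasibility rule and the repair is a matter of wording, it should be settled before the counts are examined. The mismatch in clinic names is genuine but secondary.

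**What to change.** State one 80% rule, with an explicit numerator and denominator, in identical words in protocol sections 2.0, 4.0 and 17.0 and in the SAP. Fix it before the counts are examined, and word it so that readings (c) and (d) are excluded.

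A workable default:

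- **Numerator:** unique adults who complete the NM-ASSIST.
- **Denominator:** unique adults who meet the criterion "Arrive for a clinic visit with an HIV physician" at either of the two recruiting clinics while recruitment is open, including missed cases.
- **Disclosure:** say openly that this interprets H1's total N as patients seen. Say also that it measures screening reach only, which section 25.0 treats as routine care, and not delivery of the brief intervention or the peer navigator described in section 5.0.

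If the team prefers to put the 80% on enrolled over eligible and offered, H1 must be rewritten to match. In either case, add the number screened to the steps, give Step 5 its divisor (the Step 4 count), report both rates, and reconcile the Step 1 population and the named clinic with the two recruiting clinics.

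The cost is a change of wording in four places and a count of unique patients seen at both clinics. Screening counts should be retrievable, since section 25.0 has scores entered in the electronic medical record. The reported rate may be less favourable than under another reading.

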Randomization: We will use Block random assignment (blocks of 4 by each recruitment site) to ensure equal numbers are assigned to each condition by site. Randomization should create groups with equal characteristics with respect to disease related and medical variables. However, we will assess for baseline differences prior to conducting any analyses and control as necessary.

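### Aim 2 acceptability is scored on all participants, although H2a and H2b concern SBIRT-PN patients only, and the planned HIV versus non-HIV comparison has an empty group

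*SAP*

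**What the plan says.** Acceptability belongs to the primary objective, which protocol section 1.0 gives as "Feasibility and Acceptability of intervention". The questionnaire appears under the Primary Outcome heading in protocol section 4.0 and in the SAP.

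The hypotheses in protocol section 2.0 name the population. H2a reads: "We hypothesize that SBIRT-PN will demonstrate high acceptability among patients enrolled in this condition". H2b expects that "SBIRT-PN will demonstrate higher acceptability among older HIV-positive patients enrolled in this condition".

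The analysis text does not carry that restriction. The SAP, Aim 2a and 2b, reads: "Acceptability scores will be calculated for all participants as listed above to determine overall acceptability of the SBIRT model". The Aim 2 paragraph of protocol section 17.0 has the same sentence. The decision rule is met if "80% of the participants rank the intervention as acceptable (i.e., 4 or higher) on 80% or more of the scale items". It refers to participants without naming an arm, and protocol section 4.0 words it the same way.

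The trial has two arms. Section 6.0 uses blocks of four within site "to ensure equal numbers are assigned to each condition by site", and section 10.0 sets the total: "Participants will be 90 patients recruited through DOH Columbia County and CAN Community Health".

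Both documents also plan to examine acceptability by disease type, HIV against non-HIV. Inclusion criterion 1 in protocol section 10.0 requires HIV-positive status confirmed from medical records.

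**The concern.** The hypothesis and the analysis name different populations. An analyst who follows the SAP sentence literally would pool both arms, so about half of the ratings would come from patients not assigned to the intervention being judged. Because the rule is pass/fail and part of the primary objective, those ratings could change the trial's stated conclusion about SBIRT-PN. The error can run in either direction, so pooling cannot be defended as conservative. The H2b comparison of younger and older patients would mix arms in the same way.

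The HIV versus non-HIV comparison is a separate and simpler fault: it is a planned result that can never be produced.

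**Working it through.** **Inputs.** N = 90 (protocol section 10.0). Equal allocation (section 6.0), taken as 45 per arm. The rule is at least 80% of participants rating at least 80% of items 4 or higher (protocol section 4.0; SAP). Expected dropout is 10%, with a maximum of 20% (section 25.0). The documents give no expected acceptability rate, so the true rates below are assumptions.

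**The plan's own figures.** Ten items scored 1 to 5 give totals of 10 to 50, as stated; 80% of 10 items is 8. The documents give no derivation of N = 90, so there is nothing further to reproduce.

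**Thresholds.** SBIRT-PN only: 0.80 × 45 = 36. All participants: 0.80 × 90 = 72.

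**Bounds if TAU patients also complete the form.**
- If all 45 TAU patients pass, SBIRT-PN needs only 72 − 45 = 27, and 27/45 = 60%.
- If all 45 SBIRT-PN patients pass and 26 TAU patients do, the total is 71, and 71/90 = 78.9%: fail.

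**Less extreme results.**
- SBIRT-PN 38/45 (84.4%) and TAU 33/45 (73.3%): 71/90 = 78.9%. SBIRT-PN passes alone; the pooled rule fails.
- SBIRT-PN 34/45 (75.6%) and TAU 38/45 (84.4%): 72/90 = 80.0%. SBIRT-PN fails alone; the pooled rule passes.

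**Probability of passing.** With X ~ Bin(45, p₁) for SBIRT-PN and Y ~ Bin(45, p₂) for TAU, independent and with complete forms, the two rules pass with probability P(X ≥ 36) and P(X + Y ≥ 72).

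| Assumed p₁ (SBIRT-PN) | Assumed p₂ (TAU) | SBIRT-PN only | Pooled |
|---|---|---|---|
| 0.90 | 0.85 | 0.988 | 0.986 |
| 0.85 | 0.85 | 0.873 | 0.926 |
| 0.85 | 0.75 | 0.873 | 0.563 |
| 0.85 | 0.70 | 0.873 | 0.333 |
| 0.80 | 0.80 | 0.588 | 0.563 |
| 0.75 | 0.85 | 0.280 | 0.563 |
| 0.70 | 0.90 | 0.093 | 0.563 |

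At 0.85/0.75 the probability that SBIRT-PN passes alone but fails pooled is 0.325. At 0.75/0.85 the probability that it fails alone but passes pooled is 0.304.

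**Items that do not apply to TAU.** Items 4, 5 and 8 rate the interventionist or the intervention. If TAU patients leave them blank and blanks count as not acceptable, each TAU patient reaches at most 7 of 10 items, below the 8 required. The pooled rate then cannot exceed 45/90 = 50%, and the rule cannot be met.

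**HIV versus non-HIV.** Criterion 1 makes the non-HIV group n = 0. The universal clinic screening in section 25.0 does not fill it, because enrolment still requires HIV-positive status.

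**The case against.** The best reply is that pooling was never intended. The questionnaire asks about the intervention, three of its items concern the interventionist or taking part in the intervention, and both hypotheses are limited to SBIRT-PN. In that context, all participants could mean everyone who received what is being rated. Section 6.0 does not list acceptability among the baseline or follow-up measures, and nothing says that TAU patients get the form. This reading is plausible, but neither document states it. Items on the assessor, the assessments, the staff and the overall rating could be answered in either arm. What stands is that the consequence is conditional on TAU patients completing the form.

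The second reply is that the probabilities depend on chosen rates. This is fair: at 90%/85% or 80%/80% the two rules pass almost equally often. The TAU rates in the table also require TAU patients to answer the interventionist items. The gap is large only when the arms differ and SBIRT-PN is not far from 80%, which is where a pass/fail rule matters most.

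The third reply is that the non-HIV comparison looks like leftover text and alters no primary conclusion, since the age analysis is specified separately for HIV-positive patients. That is correct. It is a line to delete and adds little weight.

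**Conclusion.** The concern holds and should be fixed. The Aim 2 analysis set in both documents does not match H2a and H2b, and the denominator of a primary pass/fail rule is undefined by arm. The mismatch and the empty non-HIV group follow from the text alone. The size of the effect rests on assumptions: TAU patients complete the form, all forms are complete, there are 45 per arm, and the true rates are as assumed. On those terms, a 10-point difference between arms moves the chance of passing from 87% to 56% (85% against 75%) or from 28% to 56% (75% against 85%). If only SBIRT-PN patients are given the form, no result changes and the correction merely states what was meant.

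**What to change.** In the Aim 2 text and the 80% rule of both documents, define the analysis set and denominator as participants randomised to SBIRT-PN. For example: *Acceptability will be calculated for participants randomised to SBIRT-PN.* Keep the age sub-analysis within that set. State whether TAU patients complete the form; if they do, report their ratings separately and descriptively, and say how items that do not apply are handled. Delete the HIV versus non-HIV comparison.

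Useful additions, though not needed to correct the mismatch: report the SBIRT-PN percentage with a 95% confidence interval and the number of missing forms, state how the missing-data plan in protocol section 17.0 applies to the rule, and add a sensitivity analysis that counts missing forms as not acceptable.

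**Cost.** Only wording changes, but precision falls. At exactly 80%, the Wilson 95% interval is 66% to 89% for 36/45, against 71% to 87% for 72/90, and the age comparison rests on about 45 patients. The sensitivity analysis is strict. If the form is collected at the last follow-up (an assumption), 10% dropout leaves 45 × 0.90 = 40.5, so 40 or 41 responders, of whom 36 (90% or 88%) must rate SBIRT-PN acceptable. At 20% dropout, 45 × 0.80 = 36, so all 36 must.
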